## Post-operative visit #1: 1 day after surgery

All participants who have undergone surgery will return after one day for standard postoperative assessment, during which they will undergo vision assessment and slit-lamp biomicroscopy. The degree of intraocular inflammation will be recorded.

## Post-operative visit #2: 1 week (±4 days) after surgery

All participants who have undergone surgery will return one week ( $\pm 4$  days) after surgery for continued evaluation and management. Vision and intraocular pressure will be assessed. Slit-lamp biomicroscopy and, when indicated, dilated eye examination will be performed to assess for inflammation in the anterior and, when indicated, posterior segments of the eye and any other ocular findings.

## Post-operative visit #3: 1 month (±14 days) after surgery

All participants who have undergone surgery will return at 1 month ( $\pm 14$  days) after surgery to undergo manifest refraction (performed according to standard procedures) to assess for best-corrected visual acuity using the ETDRS Tumbling E chart, slit-lamp biomicroscopy and dilated eye examination to assess for recurrent or persistent inflammation and any other potential ocular changes. When available, optical coherence tomography will be conducted according to standard procedures to assess for the presence of macular edema.

# Post-operative visits #4-7: 3, 6, 9, and 12 months (Visits 4 and 5 $\pm$ 21 days, Visits 6 and 7 $\pm$ 1.5 months) after surgery

All participants who have undergone surgery will return at 3 and 6 months ( $\pm 21$  days) and 9 and 12 months ( $\pm 1.5$  months) to undergo manifest refraction (performed according to standard procedures) to assess for best-corrected visual acuity, measurement of intraocular pressure, slit-lamp biomicroscopy and dilated eye examination to assess for recurrent or persistent inflammation and any other potential ocular changes. When available, optical coherence tomography will be conducted according to standard procedures to assess for the presence of macular edema.

The Month 12 visit will be the final study visit under this protocol for participants who underwent cataract surgery. For participants requiring ongoing care related to the cataract surgery both before and after the final study visit, such as those with persistent inflammation, clinical care may be

provided at a non-study site. In addition, participants who are also part of the PREVAIL III longitudinal cohort will continue to receive the yearly PREVAIL III eye exams. If participants are seen at a non-study site for eye care, the information collected will be used for this study. If there are surgical complications, participants will be referred to a study site or the LV Prasad eye clinic at JFK hospital, which has been engaged for assistance with management of complicated cases.

Any cases of persistent inflammation or any other ophthalmic concern noted at 12 months will be referred for clinical evaluation at the PREVAIL III eye clinic or the LV Prasad eye clinic. Transportation fees will be paid for participants referred to these clinics and participants will be treated free of charge.

Results of clinical tests and evaluations performed on this study will be shared with the participants during their study visits and with their health care providers if there are any results of concern that would require general medical attention.

# 4.4 End of Participation

Participants will continue to receive any needed eye care related to complications from cataract surgery for up to two years after cataract surgery on this protocol, and for the duration of PREVAIL eye care operations at JFK hospital if care is needed beyond two years. All adverse events will be followed until resolution and/or return to baseline. Clinical care visits can be conducted at sites designated to provide clinical care, while study visits will take place at designated study sites.

At the conclusion of the study, follow-up care will be arranged with an outside ophthalmologist or the participant will continue to be seen under the PREVAIL III or another protocol, if available and the participant is eligible. The participants and their physicians, with written consent, will be informed of their disease status during this study. Clinical data obtained during participation may be shared with the participants and with written permission from the participants, their private physicians. Results from the overall study may be shared once the study team has analyzed the data from all participants.

## 5.0 MANAGEMENT OF SAMPLES AND DATA

Analysis of the AC tap and lens samples will be performed at the Liberian Biomedical Research Institute and/or NIH.

# 5.1 Storage

Samples, specimens, and data collected under this protocol may be used to study eye disease in Ebola survivors. No genetic testing will be performed.

All of the stored study research samples are labeled by a code that only the investigators can link to the participant. Access to stored samples will be limited using either a locked room or a locked freezer. Data will be kept in password-protected computers. Only investigators or their designees will have access to the samples and data. Samples and data acquired under this protocol will be tracked per the PREVAIL data management system.

After two years, all protocol-derived samples will either be destroyed, or after NIH IRB and Liberian National Health Science Research Ethics Committee (Liberian Ethics Committee) approval, transferred to another existing protocol. Data will be archived by the study team in compliance with requirements for retention of research records; alternatively, after IRB and Liberian Ethics Committee approval, the data may be either destroyed or transferred to another repository.

Any loss or unanticipated destruction of samples (for example, due to freezer malfunction) or data (for example, misplacing a printout of data with identifiers) that meets the definition of a protocol deviation, unanticipated problem, and/or compromises the scientific integrity of the data collected for the study, will be reported to the IRB and Liberian Ethics Committee.

Additionally, participants may decide at any point not to have their samples stored. In this case, the principal investigator will destroy all known remaining samples and report what was done to both the participant and to the IRB and Liberian Ethics Committee.

# 5.2 Data and Sample Sharing Plan

Data and samples may also be shared with collaborating laboratories at NIH or outside of NIH and/or submitted to NIH-designated repositories and databases if consent for sharing was obtained. Repositories receiving data and/or samples from this protocol may be open-access or restricted access.

Samples and data will be stripped of identifiers and may be coded ("de-identified") or unlinked from an identifying code ("anonymized"). When coded data is shared, the key to the code will not be provided to collaborators, but will remain at NIH. Data and samples may be shared with investigators and institutions with an FWA or operating under the Declaration of Helsinki (DoH) and reported at the time of continuing review. Sharing with investigators without an FWA or not operating under the DoH will be submitted for prospective IRB approval. Submissions to NIH-sponsored or supported databases and repositories will be reported at the time of Continuing Review. Submission to non-NIH sponsored or supported databases and repositories will be submitted for prospective IRB approval.

Required approvals from the collaborating institution will be obtained and materials will be shipped in accordance with NIH and federal regulations.

Coded data and samples will also be added to the repository used by NIAID for Ebola specimens for future research.

# 6.0 RISKS/DISCOMFORTS

History and physical examination, pregnancy testing: These procedures entail minimal risk.

**Vision and IOP assessments:** These procedures entail minimal medical risk. In rare instances, the cornea may be scratched during measurement of intraocular pressure. A corneal abrasion of this sort may be painful, but it heals quickly and with no lasting effects. Treatment will be offered if needed.

**Blood draw:** Blood draws can cause discomfort and bleeding/bruising at the site of venous puncture. There is a remote risk of fainting or local infection. If any of these arise, they will be treated.

Aqueous humor sampling: Aqueous humor sampling may cause pain or discomfort in some cases, resulting from application of pressure on the eye. This typically resolves momentarily. Rare (less than 1 in 100 procedures) but potentially serious complications include lens or iris damage, endophthalmitis, corneal abscess, and blindness. To minimize risks of discomfort or damage to the lens or iris during fluid extraction, this step will be performed under an operative

microscope. If the lens is damaged, clinical judgement will guide management, with options including close observation until cataract surgery can be performed as planned, or accelerated cataract surgery if intraocular inflammation results from release of lens particles and cannot be well controlled otherwise. Aqueous humor taps pose no known additional, unique risks to Ebola survivors. It is unknown what number of subjects will have detectable Ebola viral RNA in the aqueous.

Because there is no known risk of transmitting Ebola based on presence of Ebola inside the eye, no additional safety procedures will be recommended or instituted for those who will have contact with any participants who test positive for Ebola on any tissue samples.

Cataract surgery: Risks of cataract surgery include: bleeding behind the eye as a result of anesthesia (peribulbar block), bleeding in the eye, infection (endophthalmitis), damage to intra-ocular structures including cornea and iris, and retinal detachment. Other risks include transient post-operative elevation in intraocular pressure, post-operative inflammation, macular edema, and dislocation of lens into the posterior chamber of the eye. Complications of cataract surgery can lead to worse vision or blindness. Sterile technique and antibiotics are used to minimize the chance of infection.

O Post-surgical complications: Participants will be provided with a phone number that they can call 24 hours per day, seven days per week. Anyone experiencing a post-surgical complication (such as pain in the eye or change in vision) will be told to call that number to speak with a member of the eye care team. If it is determined that the participant needs to be evaluated, they will be told where to go to be examined by one of the eye team members, and a transportation allowance will be provided for that visit. For participants from distant locations, transportation will be ensured.

Manifest refraction and optical coherence tomography: This procedure entails minimal medical risk.

**Slit-lamp biomicroscopy and dilated eye examination using direct and/or indirect:** These procedures entail minimal medical risk. The dilating drops or anesthetic drops used during the ocular examinations may sting for less than 30 seconds. They can cause an allergic reaction, and, if they are contaminated, they can cause an infection. However, neither of these problems is

likely to occur. The dilating drops can also cause a sudden increase of pressure (acute glaucoma) in eyes that are already predisposed to develop this condition. There is little risk of glaucoma being triggered in this way, but if it is, treatment is available. Exposure to lights during slit lamp and dilated eye examination can be uncomfortable.

**Potential risks for lactating women and their breastfeeding child:** There is minimal risk to the nursing infant of lactating women from the cataract surgery itself. A local peribulbar block is use for anesthesia and minimal systemic absorption is anticipated.

If a participant has significant intraocular inflammation after cataract surgery, they may require high dose oral steroids to prevent permanent vision loss from the uveitis. The steroids could theoretically pose additional risk to a breastfeeding infant. The potential risks to the nursing child are theoretical and minimal. Theoretically, infants who consume steroids in breast milk could have stomach upset, vomiting, restlessness, abnormal weight gain and increase in blood sugar, However, the amount of steroid that passes into the breastmilk is low and the risk to a breastfed infant whose mother is on steroids is low. The NIH's toxicology website states: "no adverse effects have been reported in breastfed infants with maternal use of any corticosteroid during breastfeeding". To mitigate this potential risk, nursing mothers can wait four hours after taking oral steroid medication before breast feeding their child or even choose to temporarily switch to bottle feedings until the oral dose of prednisone is 20mg/day or less.

During the consent process, breastfeeding women will be counseled regarding the potential risks of their participation on their nursing infant. Potential participants who are lactating have the option to not be in the study, or to participate in the study but temporarily stop breastfeeding if they should require high dose systemic steroids. Alternatively, they could choose to continue breastfeeding, understanding the potential risks, and mitigate the risk to the nursing child by waiting four hours after taking the oral steroid medication before breast feeding their child. Breastfeeding women will not be advised to stop or reduce breast feeding. The timing of steroids will be adjusted for nursing mothers to mitigate impact on nursing children.

## 7.0 PARTICIPANT SAFETY MONITORING

Participants will be monitored during all study visits for adverse events by the study investigators in Liberia.

# 7.1 Participant Withdrawal Criteria

Participation in the study is strictly voluntary. Participants may choose to withdraw from this study for any reason at any time without penalty, without loss of benefits or prohibition from enrolling in other clinical protocols.

An individual participant will be withdrawn for any of the following:

- An individual participant's decision. (The investigator should attempt to determine the reason for the participant's decision.)
- The investigator determines that continued participation in the study would not be in the best interest of the participant.

## 8.0 OUTCOME MEASURES

# 8.1 Primary Outcome

The primary outcomes are: 1) the proportion of EVD survivors with evidence of persistence of Ebola virus in ocular tissue and 2) comparison of the amount of intraocular inflammation, as measured by average grade of anterior chamber cell by SUN criteria, between EVD survivors and controls at 1 month and 3 months following cataract surgery.

# 8.2 Secondary Outcome

Secondary outcomes include: 1) the proportion of survivors with at least 20/40 best corrected visual acuity (BCVA) after cataract surgery, relative to controls; 2) impact of the covariates age and gender on viral persistence and cataract outcomes in EVD survivors and controls; 3) Proportion of post-operative complications in EVD survivors versus controls, as measured by clinical examination and optical coherence tomography.

# 9.0 STATISTICAL ANALYSIS

This protocol has sample sizes of convenience, in that all identified Ebola survivors who are eligible for surgery and all controls in the PREVAIL III protocol will be invited to participate, in addition to some Ebola survivors from an outlying region. Therefore, statistical analysis will be limited to what can be derived using those resultant sample sizes. Controls who are seropositive will be analyzed separately and will not serve as "controls" for statistical calculations. Similarly, seronegative survivors will not be treated as survivors in the primary analyses.

# 9.1 Analysis of Data / Study Outcomes

If all PCR results and/or immunohistochemistry results are negative, simple models which assume independence across eyes from the same individual will be used to construct a 95% confidence interval for the probability of the aqueous humor being positive and/or the lenses being positive. If some results are positive, a more sophisticated approach will be used which recognizes the potential for an association in the outcome for eyes from the same individual. Since it is possible that some individuals receiving cataract surgery in both eyes will have discordant results, generalized estimating equations with a logistic link will be used to estimate the probability of testing positive given random effects for participants. This approach can be extended to accommodate tests for effects of age and gender (which are secondary outcomes).

Study CRFs capture the grade of anterior chamber cells for each eye according to the SUN criteria. Regression models will be fit with these grades as outcome variables and survivor status, age (less than 40 or greater than or equal to 40) and gender as explanatory variables. The test of the hypothesis of no difference in grade according to survivor status will be conducted by testing the null hypothesis that the regression coefficient associated with survivor status is zero. This will be conducted at the one and three month assessments. A significance level of 0.025 will be used for both tests to account for test multiplicity. These models will also allow for testing for the effects of gender and age, which is one of the secondary objectives. The secondary outcome about having 20/40 or better BCVA after surgery will be conducted using logistic regression with explanatory variables gender, age and survivor status.

To test for differences in postoperative structural changes after intraocular surgery between survivors and controls mixed effects models will be fit to data from the one month and three month exams for central subfield thickness and intraretinal fluid cysts. These models will also control for gender and age while testing for a difference due to survivor status. Linear models will be used for central subfield thickness and logistic regression models will be used for intraretinal fluid cysts. Tests of secondary outcomes will use a significance level of 0.05.

To examine outcomes at the nine and 12 month exams, similar models will be fit but they will be extended to these later exams.

If less than 10% of participants have any cells observed in the anterior chamber, then the second primary outcome will be having cells detected (a dichotomous outcome) and the regression modeling strategy will be replaced with a logistic regression modeling approach.

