#### 3.0 PARTICIPANTS

This study involves recruiting EVD survivors and controls who have a clinical need for cataract surgery, which will be performed using the small incision cataract surgery technique which is standard practice in Liberia. Therefore, we will enroll all individuals who meet study eligibility criteria and would otherwise be eligible (clinically) to undergo cataract surgery.

The accrual ceiling is 120 people, with up to 60 EVD survivors and up to 60 controls. Current estimates of numbers of survivors and controls meeting eligibility criteria is lower, at about 35-45 survivors and 35 controls.

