# 4.3 Study Design and Procedures

In the case of Ebola survivors, if the participant has bilateral cataracts meeting inclusion criteria, the eye with worse vision will be selected for surgery. Surgery will not be performed on the second eye of seropositive survivors in the scope of this study, since optimal post-surgical management of cataract in Ebola survivors is still being established so this could pose increased risk to the participant. Surgery may be performed on the second eye of survivors confirmed via serological assessment to be seronegative. In the case of controls with bilateral cataracts meeting study criteria, the eye with worse vision will be selected as the first (and possibly only) eye to receive surgery. There is a possibility that surgical capacity will be adequate to accommodate surgery on the second eye of all control participants. If that is the case, then control participants will be offered the option of receiving surgery on their second affected eye. If the capacity does not exist to provide surgery to all control participants in that category, then it shall not be offered to any participants, in order to ensure equity of access to this potential option.

Scheduled study visits will take place at either ELWA hospital, the PREVAIL JFK eye clinic, or a mobile eye clinic staffed by study investigators to serve outlying locations. The location of any particular participant's study visit will depend on the participant's geographic location. In addition, participants requiring clinical eye care at any other time than study-directed eye visits may receive that care at additional locations to include the New Sight Eye Center in Monrovia, the L.V. Prasad Eye Clinic in Monrovia, and the eye clinic in Lofa. These additional sites are resources for the study and study participants, and the data gathered from these sites can be accessed for study purposes. All of the study and clinical care sites meet minimum requirements for performance of eye exams and are staffed by qualified eye care providers.

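### With few positive results, the logistic GEE planned for age and gender effects on viral persistence gives no valid test in either usual Wald form

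*Combined protocol and SAP*

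**What the plan says.** Section 9.1 has two branches for viral persistence. If every result is negative, a simple 95% confidence interval is given. Otherwise: "If some results are positive, a more sophisticated approach will be used". That approach is described as follows: "generalized estimating equations with a logistic link will be used to estimate the probability of testing positive given random effects for participants". The covariate tests follow from it: "This approach can be extended to accommodate tests for effects of age and gender (which are secondary outcomes". The level is set at the end of the same discussion: "Tests of secondary outcomes will use a significance level of 0.05".

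Age and gender effects on persistence are a named secondary objective (Section 2.2) and a secondary outcome (Section 8.2). Section 9.1 does not say whether the test is Wald, score or likelihood ratio, or whether standard errors are robust or model-based. It sets no minimum number of positives and no fallback if all of them share one gender or age group.

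The stated reason for GEE is that a participant's two eyes may disagree. For the survivors who form the primary set, Section 4.3 says: "Surgery will not be performed on the second eye of seropositive survivors in the scope of this study".

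**The concern.** The GEE starts at the first positive result, and the plan's own precision statement (Section 9.2) is built around none. The covariate tests would therefore probably be run on a handful of events. With a handful of events it is easy for all of them to fall in one gender or one age group. The fitted log-odds in the other group then runs towards minus infinity (separation), and the two usual GEE standard errors go in opposite directions. One makes the result overwhelmingly significant and the other makes significance impossible. The answer to this secondary objective would then depend on a software setting that the plan does not mention. Under the more common setting, an age or gender effect on Ebola persistence could be reported from one or two positive eyes with nothing behind it.

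**Working it through.** **Inputs from the documents.** Expected survivors 35-45 (Section 3.0); ceiling: "The accrual ceiling is 120 people, with up to 60 EVD survivors and up to 60 controls". One operated eye per seropositive survivor (Section 4.3). Level 0.05 (Section 9.1), taken as two-sided.

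**Assumptions.** N = 40. The documents give no gender or age split, so an even split is the base case and others are shown. Age is binary, using the coding Section 9.1 states for the cell-grade model only: "age (less than 40 or greater than or equal to 40) and gender as explanatory variables".

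**The plan's own figures.** With no positives, the exact upper 95% limit is 1 − 0.025^(1/n). This gives 0.088 for n = 40 and 0.060 for n = 60, agreeing with the 0.09 and 0.06 in Section 9.2. The plan states no operating characteristic for the age and gender tests.

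**How many positives to expect.** No true rate is given. If it is assumed to be 2-5%, the chance of one to three positives, given at least one, is 84-99% at n = 40 and 63-95% at n = 60.

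**Why the standard errors diverge.** Take a group of n with no positives and fitted probability p close to 0.
- Model-based variance of its log-odds: 1/[np(1−p)], which grows without limit.
- Robust variance: Σ(y−p)²/[np(1−p)]² = np²/[np(1−p)]², which tends to 1/n.

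For 0/20 v 2/20 the robust standard error is therefore at most about √(1/2 + 1/18 + 1/20) = 0.78. The GEE fit returned a coefficient of 22.4 with robust standard error 0.75, and a model-based standard error of about 48,300. The software marked the fit as converged, although separation warnings were printed during the simulations.

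**Chance that k positives all share one level.** With m of N in one level: [C(m,k) + C(N−m,k)]/C(N,k). For m = 20, N = 40:
- k = 2: 2×190/780 = 0.487
- k = 3: 2×1,140/9,880 = 0.231
- k = 4: 2×4,845/91,390 = 0.106
- k = 5: 2×15,504/658,008 = 0.047

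| Positives (all in one level, 20 v 20) | Chance under no effect | Robust Wald p | Model-based Wald p | Fisher p |
|---|---|---|---|---|
| 1 | 1.00 | about 1×10⁻⁹⁸ | near 1 | 1.0 |
| 2 | 0.49 | about 7×10⁻¹⁹⁸ | near 1 | 0.49 |
| 3 | 0.23 | about 5×10⁻²⁹¹ | near 1 | 0.23 |

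Tables that are not separated (1 v 1, 1 v 2, 1 v 3) do not reject. Nor does 1 v 4: the log odds ratio is log 4.75 = 1.56, the standard error √(1 + 1/19 + 1/4 + 1/16) = 1.17, and z = 1.33. At an even split, the false-positive rate of the robust Wald test is therefore the chance of separation.

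**Simulation under no effect** (600 permutations per setting, gender and age both in the model, N = 40, even split). Robust Wald rejected for each covariate in 100% of runs with one positive and 48-50% with two. Bias-reduced sandwich errors gave 100% and about 50%. Model-based Wald gave 0%.

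**Sensitivity.**
- Two positives, N = 40: 24/16 gives (276+120)/780 = 0.51; 26/14 gives (325+91)/780 = 0.53; 32/8 gives (496+28)/780 = 0.67.
- Five positives: 26/14 gives (65,780+2,002)/658,008 = 0.10, so the near-nominal 5% belongs to the even split.
- At least one of gender and age significant, two positives: about 1 − (1−0.487)² = 0.74 at even splits, up to about 0.89 at 80/20.
- Continuous age, two positives, N = 40: the age test rejected in about 23% of runs.

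**The case against.** The strongest reply is that the failing test is not in the plan. Section 9.1 names GEE with a logistic link and stops there. With two positives in one gender at 20 v 20, a score test gives p = 0.15 and a likelihood-ratio test p = 0.09, so some admissible choices do not mislead. The mention of participant random effects even leaves open whether a marginal or a mixed model is meant. This stands. A reader might infer that the planned test will be significant whenever the positives cluster, but that holds only for the robust Wald form. It does not clear the plan, because the choice between the two usual GEE forms moves p from below 10⁻⁹⁰ to near 1 on the same data.

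Second, the wording is permissive (the approach may be extended), and Section 9.0 limits analysis to what the convenience sample allows. That leaves room for description but sets no rule for it. A coefficient above 20 on two events would also strike a careful analyst, which is a safeguard of practice and not of the plan.

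Third, GEE may still be needed elsewhere. Section 4.3 allows second-eye surgery in seronegative survivors and, capacity permitting, in controls. This too stands, so the point about single eyes is confined to seropositive survivors.

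A reader might also infer that a spurious result would directly shape surgical infection control. Sections 4.3 and 11.0 say the study may inform safety standards and surgical decisions, but the surgery rule in Section 4.3 rests on detection of RNA in aqueous humor, not on age or gender.

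**Conclusion.** The concern holds in a conditional form. Section 9.1 applies a logistic GEE from the first positive result, extends it to age and gender tests at 0.05, and leaves the test, the variance estimator and the handling of sparse data open. Under robust Wald, one positive always makes a binary covariate significant. Two to five positives do so about 49%, 23%, 11% and 5% of the time per covariate under no effect. Under model-based Wald, separated data can never reject. Neither gives valid inference with few positives.

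The percentages assume N = 40 and an even split, and for age the under-40 v 40-and-over coding carried over from the cell-grade model. A single higher figure for two positives, such as 53%, would need a split near 26/14, which the documents do not give.

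This should be fixed before analysis, but it does not threaten the trial's main conclusions: the age and gender tests on persistence are secondary, and neither primary outcome is affected.

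**What to change.** In Section 9.1, replace the extension of the GEE with a named method for seropositive survivors: Fisher's exact test, or exact or Firth penalised logistic regression, with one record per survivor. State the age coding for this model. Add that when positives are very few (for example, fewer than five) the age and gender distributions are described with exact intervals and not tested. At an even 20 v 20 split that threshold loses nothing: even with four positives all in one level, Fisher's p is 0.106. If GEE is kept for sets with two operated eyes per person, name the variance estimator and the test, and remove the reference to random effects or specify a mixed model.

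The cost is a sentence or two in the plan. With very few positives the secondary objective can only be described, which is all such data support. In the seropositive survivor set no correlation between eyes is ignored, since each contributes one.
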